6.3 Statistical Analyses

6.3.1 Primary Endpoint Analysis

A linear mixed model for repeated measures (MMRM) analysis will be used for comparing each test group (Test 1 or 2) to the control group in the mean absolute change from Baseline to Week 24 (Visit 5) in each primary biomarker (WBCs, HDL-C, 8-epi-prostaglandin F_{2α}, 11-dehydrothromboxane B₂, sICAM-1, total NNAL, and COHb). In the model, study group (each of the two test group vs control), visit, and study group by visit interaction, gender, age class (less than 45 years or greater or equal to 45 years), and BMI class (less than 25 kg/m² or greater or equal to 25 kg/m²) are the fixed effect factors. The baseline value of the response biomarker, where baseline is defined as the value reported on Day 1 (Week 1) of the 12-week ALCS-RA-16-06-EV study (CA20130), is the fixed effect covariate and subject is the random effect factor. A restricted maximum likelihood estimation method will be applied and several covariance structures will be tried. Five candidate covariance structures will be considered: compound symmetry, first order autoregressive, first order autoregressive with a random subject effect, unstructured and Toeplitz. The most appropriate covariance structure will be determined based on the AIC criteria (the covariance structure with the smallest AIC will be chosen). If the model cannot be converged, a robust sandwich estimator for the standard error of the fixed effects will be used. The least-square mean difference, 95% confidence interval and p-value will be provided for the group difference. Pairwise comparisons (Test 1 vs. control, and Test 2 vs. control) will be performed using a Dunnett's test at a 2-sided significance level of 0.05 to adjust for multiplicity. The analysis will be conducted on the mITT and PP datasets.

The following SAS codes will be used to perform the analysis.

```
Proc mixed data=<>;
Class subject gender group visit age bmi;
Model response = gender group visit group*visit age bmi baseline/ddfm=kr;
Repeated visit/type=<type> subject=subject;
LSmeans group*visit/CL alpha=0.05 pdiff dunnett('CONTROL');
Run;
```

Note: This model will include both the Week 24 value (primary endpoint) and Week 18 value (secondary endpoint). The above analysis will also output the residual diagnosis to check for normality and to identify outliers).

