6.3.2 Secondary Endpoint Analysis

The same statistical analysis model defined in the primary analysis Section 6.3.2 will also be used to make the following comparisons for the primary biomarkers (WBCs, HDL-C, 8-epi-prostaglandin F_{2α}, 11-dehydrothromboxane B₂, sICAM-1, total NNAL, and COHb):

- absolute change from Baseline to Week 24 between the combined e-vapor use group (Test 1 + Test 2) and the Control group.
- absolute change from Baseline to Week 24 between the two test groups (Test 1 vs Test 2).
- absolute change from Baseline to Week 18 between each Test group and the Control group.

The above analyses will be conducted on the mITT datasets.

The same statistical analysis model defined in the primary analysis Section 6.3.2 will also be used for assessment of:

- changes in percent of predicted FEV1, FVC, and FEV1/FVC ratios from Baseline [Screening (Visit 2) of the 12 week ALCS-RA-16-06-EV study (CA20130)] to Week 18 and Week 24 between each Test Group and the Control group.

The analysis of pulmonary function parameters will be conducted on the dataset of subjects with a valid baseline and at least one valid post baseline spirometry assessment. In addition, a PP dataset for pulmonary function parameters will be created from the subjects with valid baseline and post baseline spirometry data using the criteria for the PP population in Section 4, and the analysis will be conducted on this dataset.

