| Test 1 | XX | X.XX | XX.XX - XXX.XX | X.XXXX |
| Test 2 | XX | X.XX | XX.XX - XXX.XX | X.XXXX |
| Control | XX | X.XX | XX.XX - XXX.XX | X.XXXX |

Note: The mixed model for repeated measures includes study group, study visit, study group by study visit interaction, gender, age class, BMI class, baseline value as the covariate, and subject as the random effect, with a variance-covariance matrix based on the AIC value. < > variance-covariance structure is used for the final model.

n = Number of observation used in the analysis

Least-squares means (LS Means) are calculated from the MMRM.

Baseline = Day 1 (week 1) of the 12-week ALCS-RA-16-06-EV study (CA20130)
Visit 5 = Week 24 (Day 168 ± 3)

Test 1 Group = e-Vapor Product XLCB

Test 2 Group = e-Vapor Product XLMB

Control Group = Continue smoking lit-end conventional cigarette

Program: /CAXXXX/sas_prg/pksas PROGRAMNAME.SAS DDMMYYYY HH:MM

Programmer Note: Tables 14.2.1.X.12.1 (mITT Population with BLQ values set to the LLOQ) will only be presented if the percentage of values that are BLQ is greater than 5% of observations.

Note: Statistical comparison Tables 14.2.1.1.4.2, 14.2.1.2.4.2, 14.2.1.3.4.2, 14.2.1.4.4.2, 14.2.1.5.4.2, 14.2.1.6.4.2, 14.2.1.7.4.2, 14.2.1.8.5 will have the following format:

Page 1 of X
 Table 14.2.1.1.4.2 Statistical Comparisons of <Biomarker> Absolute Change From Baseline (Units) Between Study Groups by Visit (mITT Population)

| Comparison | Visit | LS Means | | LS Mean Difference (Test - Reference) | XX% Confidence Interval | p-value |
|----------------------------|-------|----------|---------------|--|-------------------------|---------|
| | | Test (n) | Reference (n) | | | |
| Test 1 vs Control | 3 | X.XX (X) | X.XX (X) | XXX.XX | XX.XX - XXX.XX | X.XXXX |
| | 5 | X.XX (X) | X.XX (X) | XXX.XX | XX.XX - XXX.XX | X.XXXX |
| Test 2 vs Control | 3 | X.XX (X) | X.XX (X) | XXX.XX | XX.XX - XXX.XX | X.XXXX |
| | 5 | X.XX (X) | X.XX (X) | XXX.XX | XX.XX - XXX.XX | X.XXXX |
| Test 1 + Test 2 vs Control | 5 | X.XX (X) | X.XX (X) | XXX.XX | XX.XX - XXX.XX | X.XXXX |
| Test 1 vs Test 2 | 5 | X.XX (X) | X.XX (X) | XXX.XX | XX.XX - XXX.XX | X.XXXX |

Note: The mixed model for repeated measures includes study group, study visit, study group by study visit interaction, gender, age class, BMI class, baseline value as the covariate, and subject as the random effect, with a variance-covariance matrix based on the AIC value. < > variance-covariance structure is used for the final model.

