Least-squares means (LS Means) are calculated from the MMRM.

Test = First group in the comparison

Reference = Second group in the comparison

n = Number of observation used in the analysis

Baseline = Day 1 (week 1) of the 12-week ALCS-RA-16-06-EV study (CA20130)

Visit 3 = Week 18 (Day 126 ± 3)

Visit 5 = Week 24 (Day 168 ± 3)

Test 1 Group = e-Vapor Product XLCB

Test 2 Group = e-Vapor Product XLMB

Test 1 + Test 2 Group = Combined e-Vapor Use Group

Control Group = Continue smoking lit-end conventional cigarette

Program: /CAXXXX/sas_prg/pksas PROGRAMNAME.SAS DDMMYYYY HH:MM

Note: Statistical comparison tables for PP population, mITT with imputation populations, and mITT population with outliers excluded, and mITT Population with BLQ values set to the LLOQ: 14.2.1.1.5.2, 14.2.1.1.10.2, 14.2.1.1.11.3, 14.2.1.1.12.2, 14.2.1.2.5.2, 14.2.1.2.10.2, 14.2.1.2.11.3, 14.2.1.2.12.2, 14.2.1.3.5.2, 14.2.1.3.10.2, 14.2.1.3.11.3, 14.2.1.3.12.2, 14.2.1.4.5.2, 14.2.1.4.10.2, 14.2.1.4.11.3, 14.2.1.4.12.2, 14.2.1.5.5.2, 14.2.1.5.10.2, 14.2.1.5.11.3, 14.2.1.5.12.2, 14.2.1.5.13.2, 14.2.1.7.12.2, will have the following format:

Page 1 of X
Table 14.2.1.1.5.2 Statistical Comparisons of <Biomarker> Absolute Change From Baseline to Visit 5 (Units) Between Study Groups (<Population>)

| Comparison | LS Means | | LS Mean Difference (Test - Reference) | XX% Confidence Interval | p-value |
|-------------------|----------|---------------|--|-------------------------|---------|
| | Test (n) | Reference (n) | | | |
| Test 1 vs Control | X.XX (X) | X.XX (X) | XXX.XX | XX.XX - XXX.XX | X.XXXX |
| Test 2 vs Control | X.XX (X) | X.XX (X) | XXX.XX | XX.XX - XXX.XX | X.XXXX |

Note: The mixed model for repeated measures includes study group, study visit, study group by study visit interaction, gender, age class, BMI class, baseline value as the covariate, and subject as the random effect, with a variance-covariance matrix based on the AIC value. Least-squares means (LS Means) are calculated from the MMRM.

Test = First group in the comparison

Reference = Second group in the comparison

n = Number of observation used in the analysis

Baseline = Day 1 (Week 1) of the 12 week ALCS RA 16 06 EV study (CA20130)

Visit 5 = Week 24 (Day 168 ± 3)

Test 1 Group = e-Vapor Product XLCB

Test 2 Group = e-Vapor Product XLMB

Program: /CAXXXX/sas_prg/pksas PROGRAMNAME.SAS DDMMYYYY HH:MM

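### The primary SAS code puts Dunnett's adjustment on group-by-visit cells without naming a visit, so it does not specify the two-comparison Week 24 test in the prose

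*SAP*

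**What the plan says.** Section 6.3.1 of the SAP names the primary comparison as each Test group against Control in change from Baseline to Week 24 (Visit 5), for seven biomarkers. On multiplicity it says: "Pairwise comparisons (Test 1 vs. control, and Test 2 vs. control) will be performed using a Dunnett's test", at a two-sided level of 0.05. On reporting it says: "The least-square mean difference, 95% confidence interval and p-value will be provided for the group difference".

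The section then gives SAS code and states that this code will be used. The line that produces the comparisons begins "LSmeans group*visit/CL alpha=0.05 pdiff dunnett('CONTROL". A note under the code adds: "This model will include both the Week 24 value (primary endpoint) and Week 18 value (secondary endpoint".

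Section 6.3.2 takes a further set of comparisons from the same model, among them "absolute change from Baseline to Week 18 between each Test group and the Control group".

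Two comparison shells in Section 10 matter here:
- Table 14.2.1.1.4.2 ("Absolute Change From Baseline (Units) Between Study Groups by Visit (mITT Population") has rows for Test 1 and Test 2 against Control at Visit 3 and at Visit 5. It adds the combined group against Control, and Test 1 against Test 2, at Visit 5 only.
- Table 14.2.1.1.5.2 ("Absolute Change From Baseline to Visit 5 (Units) Between Study Groups (<Population>") has only the two Test-against-Control rows.

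Both head the interval column "XX% Confidence Interval". Neither mentions Dunnett.

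**The concern.** The prose describes a family of two comparisons at one visit. The code applies the adjustment to an effect that spans both visits and gives a control label that is a level of group, not a group-by-visit cell. There is a Control cell at each visit, so the label does not identify the reference, and nothing in the line limits the family to Week 24.

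The adjusted p-values and adjusted limits for all seven primary biomarkers, in both the mITT and PP analyses, depend on what the family is. If the secondary Week 18 values enter it, the primary test becomes stricter than the plan states. If a programmer repairs the line informally, the family and the type of interval are chosen outside the plan.

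**Working it through.** **What the line covers.** Three groups by two visits gives 3 × 2 = 6 cells and 6 × 5 / 2 = 15 possible pairwise differences. Against a single Control cell there are 5 comparisons.
- With Control at Visit 5 as reference, two of the five are the planned ones. The other three are Test 1 at Week 18, Test 2 at Week 18 and Control at Week 18, each against Control at Week 24.
- With Control at Visit 3 as reference, none of the five is a same-visit Week 24 comparison.

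**Whether another section settles it.** No. Section 6.3.2 does not say whether the Week 18 comparisons share the Dunnett family. The shells show which rows are reported, not which p-values are adjusted or over what family. Section 6.3.3 uses the same LSmeans line without the Dunnett option, so its presence in 6.3.1 is a deliberate choice.

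**Inputs for the size.**
- Group sizes 50, 48 and 52 for Test 1, Test 2 and Control (Section 3).
- Two-sided 0.05 (Section 6.3.1).
- Assumed: no dropout, equal variances, and 150 − 7 = 143 degrees of freedom (intercept, two group terms, gender, age class, BMI class, baseline).
- Assumed: Week 18 to Week 24 correlation ρ from 0 to 0.9, because the SAP gives none.

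The SAP states no critical value or power, so there is no figure of its own to reproduce.

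**Intended test.** The correlation between the two Test-against-Control statistics at one visit is √[50 × 48 / ((50 + 52)(48 + 52))] = √(2400 / 10200) = 0.485. The two-sided 5% point of the bivariate t with this correlation is |t| = 2.236. The matching unadjusted p-value is 0.0269.

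**Alternative families.** These come from simulating the multivariate t with 10^6 draws. The error is the probability, under no effect, that at least one of the two Week 24 comparisons exceeds the critical value.

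| ρ | Four same-visit comparisons: critical \|t\| | Error of Week 24 pair | Five cells vs Control at Week 24: critical \|t\| | Error of Week 24 pair |
|---|---|---|---|---|
| 0 | 2.505 | 0.0255 | 2.546 | 0.0228 |
| 0.3 | 2.496 | 0.0258 | 2.539 | 0.0230 |
| 0.5 | 2.482 | 0.0269 | 2.530 | 0.0237 |
| 0.7 | 2.454 | 0.0291 | 2.513 | 0.0248 |
| 0.9 | 2.382 | 0.0345 | 2.475 | 0.0272 |

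Dunnett applied within each visit stays at 2.23 to 2.24 at both weeks for every ρ. Across the table, the unadjusted p threshold falls from 0.0269 to between 0.0185 (|t| = 2.382) and 0.0120 (|t| = 2.546). Adjusted limits are 7% to 14% wider. A second run with 140 degrees of freedom gave the same picture: 2.24 for the pair, 2.39 to 2.50 for four, and 2.48 to 2.54 for five (ρ from 0.3 to 0.9).

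**Power, Test 1 against Control.** The standard error in residual SD units is √(1/50 + 1/52) = 0.198. By the non-central t:
- 80% power at 2.236 needs non-centrality 3.081, a difference of 3.081 × 0.198 = 0.61 SD. Power is then 75.7% at 2.382 and 70.3% at 2.546.
- 90% power needs non-centrality 3.525, or 0.70 SD. Power is then 87.2% and 83.5%.

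**Adjusted or unadjusted interval.** The unadjusted critical value is 1.977 (140 degrees of freedom), so Dunnett limits are 2.236 / 1.977 = 1.13 times as wide. A result with unadjusted p between about 0.027 and 0.05 would show an unadjusted interval that excludes zero beside an adjusted p above 0.05.

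**The case against.** The strongest reply is that the test is specified. The prose fixes the comparisons, the method, the level and the time point, and the shells pair each Test group with Control at the same visit. The code is visibly a template: it has placeholders for the data set and covariance type, and no statement for the combined-group contrast that Section 6.3.2 takes from the same model. A programmer must complete it from the prose, and if the line is corrected that way, nothing is lost. The four- and five-comparison families are readings that the SAP never states. The SAP also describes the analysis as largely exploratory and states no adjustment across the seven biomarkers.

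Much of this stands. The intent can be recovered, and the figures above are conditional on the reading. A loss of power without inflation of error holds for the two readings computed, not for every possible outcome of the line: if no adjustment were applied at all, the error of the primary pair would be about 9.1%. SAS was not available, so the claim concerns what the line specifies, not what it would output. The placeholder in the interval heading is ordinary shell practice, and the 95% level is fixed in Section 6.3.1; only adjusted versus unadjusted is open.

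The reply does not remove the mismatch. The code is prescribed, and no other section corrects it. Section 4 requires deviations from the approved SAP to be reported, so even the right repair would depart from the plan as written.

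**Conclusion.** The concern holds. The prescribed primary-analysis code does not specify the test that the prose of Section 6.3.1 defines, and the SAP does not say which 95% limits accompany the adjusted p-values. The mismatch follows from the SAP's own text and is certain. Its size is conditional on the assumed degrees of freedom, the absence of dropout, the between-visit correlation and the family chosen. On the readings computed, the plan would run the primary pair at about half to two-thirds of its stated 5% error and give up roughly 4 to 10 points of power at a difference of 0.61 SD. Estimated differences are unaffected. It should be corrected before analysis, and the exploratory setting limits how much depends on it.

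**What to change.** In Section 6.3.1, replace the LSmeans line with code that forms Test 1 against Control and Test 2 against Control at Week 24 and applies a Dunnett adjustment over those two only. Produce the Week 18 pair in a separate within-visit step, and say in Section 6.3.2 whether that pair is Dunnett-adjusted as its own family. Add one sentence stating that the 95% intervals for the primary comparisons are the Dunnett-adjusted limits that match the adjusted p-values, and footnote the comparison shells accordingly. Run the new code on dummy data to confirm that exactly two comparisons enter the Week 24 adjustment.

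The cost is a few lines of SAS code, one or two sentences of SAP text and a shell footnote. No data collection or model term changes.

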6.3.1.1 Dealing with non-normality

A standard residual analysis using Proc Mixed procedure will be used to examine validity of normality assumptions for the primary endpoints including WBCs, HDL-C, 8-epi-prostaglandin F_{2α}, 11-dehydrothromboxane B₂, sICAM-1, total NNAL, and COHb. A natural logarithmic transformation will be applied to the endpoint in the linear mixed model if the normality assumption does not hold.

6.3.2 Secondary Endpoint Analysis

The same statistical analysis model defined in the primary analysis Section 6.3.2 will also be used to make the following comparisons for the primary biomarkers (WBCs, HDL-C, 8-epi-prostaglandin F_{2α}, 11-dehydrothromboxane B₂, sICAM-1, total NNAL, and COHb):

- absolute change from Baseline to Week 24 between the combined e-vapor use group (Test 1 + Test 2) and the Control group.
- absolute change from Baseline to Week 24 between the two test groups (Test 1 vs Test 2).
- absolute change from Baseline to Week 18 between each Test group and the Control group.

The above analyses will be conducted on the mITT datasets.

The same statistical analysis model defined in the primary analysis Section 6.3.2 will also be used for assessment of:

- changes in percent of predicted FEV1, FVC, and FEV1/FVC ratios from Baseline [Screening (Visit 2) of the 12 week ALCS-RA-16-06-EV study (CA20130)] to Week 18 and Week 24 between each Test Group and the Control group.

The analysis of pulmonary function parameters will be conducted on the dataset of subjects with a valid baseline and at least one valid post baseline spirometry assessment. In addition, a PP dataset for pulmonary function parameters will be created from the subjects with valid baseline and post baseline spirometry data using the criteria for the PP population in Section 4, and the analysis will be conducted on this dataset.

6.3.3 Exploratory Endpoint Analysis

The same statistical analysis model defined in the primary analysis Section 6.3.2 will also be used for the exploratory analysis to provide estimates for:

- Absolute changes in urine nicotine equivalents (NE) from Baseline to Week 18 and Week 24 between the each Test Group and the Control group and between the combined e-vapor use group (Test 1 + Test 2) and the Control group (mITT population).

For the following endpoints, the same statistical analysis model defined in the primary analysis Section 6.3.2 but without the fixed effect of BMI will be used for the exploratory analysis to evaluate:

- absolute changes in the QGEN and TQOLIT questionnaire responses from Baseline to Week 18 and Week 24 between the each Test Group and the Control group.

The following SAS codes will be used to perform the analysis:

```
Proc mixed data=<>;
Class subject gender group visit age;
Model response = gender group visit group*visit age baseline/ddfm=kr;
Repeated visit/type=<type> subject=subject;
LSmeans group*visit/CL alpha=0.05 pdiff;
Run;
```

For the endpoints with only Baseline and Week 24 measurements, an ANCOVA model will be used for the exploratory analysis to evaluate:

- absolute changes in the mCEQ factor score from Baseline to Week 24 in the Test and Control groups.

In the model, study group, gender, and age class (less than 45 years or greater or equal to 45 years) are the fixed effect factors. The baseline [Day 1 (Week 1) of the 12-week ALCS-RA-16-06-EV study (CA20130)] value of the measurement is the fixed effect covariate.

The following SAS codes will be used to perform the analysis:

```
proc mixed data=<>;
class subject gender group age;
model testname = gender group age baseline;
lsmeans group/diff cl alpha=0.05;
run;
```

Responses to the Reasons of Use/Not-Use Test Product questionnaire will be summarized using frequency count tables for each question.

Questionnaire analyses will be conducted using the dataset of subjects with a baseline and at least one post-baseline response for each individual question.

6.3.4 Subgroup Analysis

Subgroup analysis will depend on subgroup sample sizes. Descriptive statistics will be provided for absolute change from Baseline* to Week 24 in all primary endpoints by study group, gender, age class (less than 45 years or greater or equal to 45 years and BMI class (less than 25 kg/m² or greater or equal to 25 kg/m²). These analyses will be based on the mITT dataset.

The subgroup analysis using MMRM will be conducted for the difference in absolute change from Baseline* to Week 24 by gender, age class and BMI class if the subgroup factor (gender, age class, or BMI class) in the model is statistically significant and if the sample sizes are appropriate (n>=15 in each subgroup cell). The subgroup analysis will be conducted on the mITT dataset.

The same statistical analysis model in the primary analysis will be used for subgroup analysis. An additional fixed effect, study group by subgroup interaction (gender, age class, or BMI class), will be included in the statistical analysis model.

*Baseline values reported on Day 1 (Week 1) of the 12-week ALCS-RA-16-06-EV study (CA20130) will be used.

6.3.5 Sensitivity Analysis

6.3.5.1 Analysis Variables for Sensitivity Analysis

The sensitivity analysis will be performed for primary endpoints (absolute change from baseline to Week 24 in whole blood WBC count, serum HDL-C concentration, creatinine-adjusted urine 8-epi-prostaglandin F_{2a}, creatinine-adjusted urinary 11-dehydrothromboxane B₂, serum sICAM-1, creatinine-adjusted total NNAL, and whole blood COHb).

6.3.5.2 Handling of Missing Data

The last observation (Baseline value or Week 18 value) carried forward method will be applied to the mITT population to assess the effect of missing data.

6.3.5.3 Examining Influence of Outliers

Data outliers will be examined through Proc Mixed model residual diagnosis (+/- 4 studentized residuals). The outlier test results will be conducted for the primary endpoints (absolute change from baseline to Week 24 in whole blood WBC count, serum HDL-C concentration, creatinine-adjusted urine 8-epi-prostaglandin F_{2a},

creatinine-adjusted urine 11-dehydrothromboxane B₂, serum sICAM-1, creatinine-adjusted total NNAL, and whole blood COHb). A sensitivity analysis by excluding outliers will be performed for the primary analysis variables at Visit 5 (Week 24) if any outliers are found using the above criteria.

6.3.5.4 Handling BLQ values

Values BLQ for nicotine and its metabolites, COHb, NNAL, NNN, 8-epi-prostaglandin F_{2 α} , 11-dehydrothromboxane B₂, and sICAM-1 will be presented in the data listings as BLQ. Values BLQ for nicotine and metabolites will be set to one-half of the limit of quantitation prior use in the calculation of nicotine equivalents and data analysis of NE. Values BLQ for NNAL, NNN, 8-epi-prostaglandin F_{2 α} , 11-dehydrothromboxane B₂, sICAM-1 and COHb will be set to one-half of the LLOQ prior to data analysis. A sensitivity analysis of the primary endpoint analysis will be conducted by setting the BLQ value to the LLOQ if the percentage of values that are BLQ is greater than 5% of observations. The sensitivity analysis for NE will be conducted if the percentage of observations that are BLQ is greater than 5% for any one of the NE components. LLOQ values for each analyte are shown in the table below.

| Analyte | LLOQ |
|--------------------------------------|-------------|
| Nicotine | 50.0 ng/mL |
| Cotinine | 50.0 ng/mL |
| trans-3'-hydroxycotinine | 50.0 ng/mL |
| nicotine glucuronide | 50.0 ng/mL |
| cotinine glucuronide | 200 ng/mL |
| trans-3'-hydroxycotinine glucuronide | 200 ng/mL |
| NNN | 0.200 pg/mL |
| NNAL | 5.00 pg/mL |
| 11-dehydrothromboxane B2 | 25.0 pg/mL |
| 8-epi-prostaglandin F2 α | 25.0 pg/mL |
| sICAM-1 | 12.5 ng/mL |
| COHb | 0.2% |

